Patient who performed V2 (3-months), V3 (6-months), V4 (9-months), V5 (12-months) follow up visit

At each follow up visit they will be defined as patients satisfying the following criteria:

1. Patients evaluable at enrollment (i.e., responding to criteria of par 2.1 Patients evaluable at enrollment)

2. Data collected at x-month follow-up = "Yes" **[F16_PATIENT_DISPOSITION, 3 month f-up.PD_1; 6 month f-up.PD_1; 9 month f-up.PD_1; 12 month f-up.PD_1]**
where x=3-, 6-, 9-, 12-
3. Follow-up performed at $x \pm 1.5$ months from enrollment (where x=3-, 6-, 9-, 12-)
 - (Date of follow up visit (dd/mmm/yyyy) **[F16_PATIENT_DISPOSITION, 3 month f-up.PD_2; 6 month f-up.PD_2; 9 month f-up.PD_2; 12 month f-up.PD_2]**– Date of enrolment visit (dd/mm/yyyy) **[_PatientInfo. Date_enrollment]**) $/30.4375 \geq 1.5$ (or 4.5 or 7.5 or 10.5))
AND
 - (Date of follow up visit (dd/mmm/yyyy) **[F16_PATIENT_DISPOSITION, 3 month f-up.PD_2]**– Date of enrolment visit (dd/mm/yyyy) **[_PatientInfo. Date_enrollment]**) $/30.4375 \leq 4.5$ (or 7.5 or 10.5 or 13.5))
4. With available IPF symptoms evaluation at baseline and at $x \pm 1.5$ months from enrollment (where x=3-, 6-, 9-, 12-)
 - (IPF symptoms at baseline ? **[F06_IPF_SYMPTOMS.SYM_IPF_symptoms_YN]**=No OR (IPF symptoms at baseline?=Yes AND at least one symptom **[F06_IPF_SYMPTOMS.SYM_IPF_symptoms, SYM_IPF_symptoms_other]** not missing))
AND
 - (IPF symptoms at x-month follow up? **[F06_IPF_SYMPTOMS.SYM_IPF_symptoms_YN]**=No OR (IPF symptoms at x-month follow up?=Yes AND at least one symptom **[F06_IPF_SYMPTOMS.SYM_IPF_symptoms, SYM_IPF_symptoms_other]** not missing))
where x=3-, 6-, 9-, 12-

IPF symptoms

For patients with *if other symptom, specify* **[F06_IPF_SYMPTOMS.SYM_IPF_symptoms, SYM_IPF_symptoms_other]** =EXERTIONAL DYSPNEA or DISABLING DYSPNEA the field will be considered as DYSPNEA.

Incident IPF symptom at x-month follow up

IPF symptom absent at enrollment visit and present at x-month follow-up visit) **[F06_IPF_SYMPTOMS.SYM_IPF_symptoms]**
Where x=3-, 6-, 9-, 12-

Patients with incident IPF symptom at x-month follow up

Patients with incident IPF symptom (according to previous definition) over total number of patients without symptom at baseline.
Where x=3-, 6-, 9-, 12-

Remitted IPF symptom at x-month follow up

IPF symptom present at enrollment visit and absent at x-month follow-up visit) **[F06_IPF_SYMPTOMS.SYM_IPF_symptoms]**
Where x=3-, 6-, 9-, 12-

Patients with remitted IPF symptom at x-month follow up

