All IPF pharmacological treatments having (Start date of therapy (dd/mmm/yyyy) **[F23_IPF_PHARMACOLOGICAL_THERAPY.START_DATE_THER]** >= date of first IPF diagnosis (mm/yyyy) **[F05_DIAGNOSIS_IPF.DIA.Date_IPF_diagnosis]** AND Start date of therapy (dd/mmm/yyyy) < Date of enrollment visit) AND (end date (dd/mmm/yyyy) **[F23_IPF_PHARMACOLOGICAL_THERAPY.END_DATE_THER]** > Date of enrollment visit (dd/mmm/yyyy) **[PatientInfo.Date_enrollment]** OR (end date missing AND "Ongoing at the end of observation?" = "Yes")) will be considered.

Drug names will be coded by CDM in actives.

IPF pharmacological treatments ongoing at 3, 6 and 12-month follow-up visit

IPF pharmacological treatments from diagnosis and ongoing at 3-, 6- or 12-month follow up will be defined as follows.

At each follow-up visit all treatments having (start date **[F23_IPF_PHARMACOLOGICAL_THERAPY.START_DATE_THER]** >= date of first IPF diagnosis (mm/yyyy) **[F05_DIAGNOSIS_IPF.DIA.Date_IPF_diagnosis]** AND < date of follow-up visit) AND ((end date **[F23_IPF_PHARMACOLOGICAL_THERAPY.END_DATE_THER]** >= date of first IPF diagnosis (mm/yyyy) **[F05_DIAGNOSIS_IPF.DIA.Date_IPF_diagnosis]** AND end date > date of follow-up visit **[F16_PATIENT_DISPPOSITION.PD_2]**) OR (end date = missing and "Ongoing at the end of observation?" = "Yes" **[F23_IPF_PHARMACOLOGICAL_THERAPY.ONGOING_THER]**) will be selected.

IPF non-pharmacological therapy ongoing at enrollment

IPF non pharmacological treatments from diagnosis and ongoing at enrollment will be defined as follows.

All IPF non-pharmacological therapy having (Start date of therapy (dd/MMM/yyyy) **[F24_NON_PHARMACOLOGICAL_THERAPY.START_DATE_NF]** >= date of first IPF diagnosis (mm/yyyy) **[F05_DIAGNOSIS_IPF.DIA_Date_IPF_diagnosis]** AND Start date of therapy (dd/MMM/yyyy) < Date of enrollment visit) AND (end date (dd/MMM/yyyy) **[F24_NON_PHARMACOLOGICAL_THERAPY.END_DATE_NF]** > Date of enrollment visit (dd/MMM/yyyy) **[PatientInfo.Date_enrollment]**) OR (missing and "Ongoing at the end of observation?" **[F24_NON_PHARMACOLOGICAL_THERAPY.ONGOING_NF_THER]** = "Yes")) will be considered.

For patients receiving more than one therapy, combination of therapies will be reported (e.g. Long-term oxygen therapy + Cardiopulmonary exercise training).

IPF non pharmacological treatments ongoing at 3-, 6- and 12-month follow-up visit

IPF non pharmacological treatments from diagnosis and ongoing at 3-, 6- or 12-month follow up will be defined as follows.

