4 CONTENTS

The tables to be produced for interim report are in green (if analysis of follow up data is planned, data collected up to 3-month follow up will be considered).

Missing data will not be imputed and so patients with missing data will be excluded from the analyses of that variable(s).

If the investigator is unable to collect the requested information the data will be "NK" (Not Known) or "NA" (Not Available), if the investigator did not record the information the data will be "Not Recorded".

4.1 *Patient disposition*

Table 1. Enrolled and evaluable patients

The table will provide absolute and relative frequencies of:

- patients enrolled in the FIBRONET study
- patients evaluable at enrollment (as described in par. 2.1)
- patients who performed V2 (3 ± 1.5 months)
- patients who performed V3 (6 ± 1.5 months)
- patients who performed V4 (9 ± 1.5 months)
- patients who performed V5 (12 ± 1.5 months)

The percentages will be computed over the total number of enrolled patients.

Table 2. Reasons for non-eligibility to analyses

The table will describe the reasons for patient non-eligibility at enrollment.

Absolute and relative frequency distribution will be performed; the percentages will be computed out of the total number of enrolled patients.

Table 3. Premature study termination

The table will describe the distribution of patients withdrawn from the study ("Did the patient complete the study?"

[\[F19_STUDY_COMPLETION.SC_1\]](#) = "No") and the reasons for premature study termination ("Cause of drop out" [\[F19_STUDY_COMPLETION.SC_2\]](#)).

Absolute and relative frequency distribution will be performed; as for withdrawal, percentages will be computed out of the total number of patients evaluable at enrollment.

As regards reasons of withdrawal, the percentages will be computed out of the total number of patients withdrawn from the study. A patient could withdraw from the study for more than one reason.

The distribution of patients withdrawn for other reasons will be also reported in a separate table ("If other cause, specify:" ≠ missing [\[F19_STUDY_COMPLETION.SC_3\]](#)), if other reason frequency will be >20%.

Table 4. Months between baseline and follow up visits

The table will provide main descriptive statistics (mean, median, standard deviation, quartiles, min, max) of time (months) between baseline and each follow up visit.

Patients who performed each follow up visit will be considered.

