4.4 Primary objective: Clinical course of IPF during observation**Table 13. IPF symptoms**

The table will provide at enrollment and at V2, V3, V4, V5:

- Frequency distribution of patients with at least one IPF symptom [\[F06_IPF_SYMPTOMS.SYM_IPF_symptoms_YN\]](#)
- Frequency distribution of IPF symptoms [\[F06_IPF_SYMPTOMS.SYM_IPF_symptoms\]](#)

Descriptives will be computed out of the total number of patients who performed the specific visit.

Table 20. Lung Function Assessments – Spirometry at each study visit and variation during observation period

The table will provide at enrollment, V2, V3, V4, V5 main descriptive statistics (mean, median, standard deviation, quartiles, min, max) of:

- FEV1 (L) [\[F07_LUNG_FUNCTION_ASS.LU_FEV1\]](#)
- FEV1 of the predicted (%) [\[F07_LUNG_FUNCTION_ASS.LU_FEV1_predicted\]](#)
- FVC (L) [\[F07_LUNG_FUNCTION_ASS.LU_FVC\]](#)
- FVC of the predicted (%)
- FEV1/FVC (%) [\[F07_LUNG_FUNCTION_ASS.LU_FEV1_FVC\]](#)

- Total lung capacity (L) [\[F07_LUNG_FUNCTION_ASS.LU_TLC_Num\]](#)
- DLCO [\[F07_LUNG_FUNCTION_ASS.LU_DLCO_Num\]](#), along with the respective DLCO unit [\[F07_LUNG_FUNCTION_ASS.LU_DLCO_unit\]](#).
- DLCO of the predicted (%) [\[F07_LUNG_FUNCTION_ASS.LU_DLCO_Predicted_Num\]](#)
- SaO2 (%) [\[F07_LUNG_FUNCTION_ASS.LU_SAO2_Num\]](#)
- change at each follow-up visit vs baseline of FEV1 (L)
- change at each follow-up visit vs baseline of FEV1 of the predicted (%)
- change at each follow-up visit vs baseline of FVC (L)
- (absolute and relative) change at each follow-up visit vs baseline of FVC of the predicted (%)
- change at each follow-up visit vs baseline of FEV1/FVC (%)

- change at each follow-up visit vs baseline of Total lung capacity (L)
- change at each follow-up visit vs baseline of DLCO, along with the respective DLCO unit
- change at each follow-up visit vs baseline of DLCO of the predicted (%)
- change at each follow-up visit vs baseline of SaO2 (%)

Evaluable patients at the specific visit with spirometry performed [\[F07_LUNG_FUNCTION_ASS.LU_spirometry_YN\]](#) at study visit or in the previous 3 months will be considered.

Table 21. Lung Function Assessments – Emogas analysis at each study visit and variation during observation period

The table will provide at enrollment, V2, V3, V4, V5 the main descriptive statistics (mean, median, standard deviation, quartiles, min, max) of:

- PO2 (mmHg) [\[F07_LUNG_FUNCTION_ASS.LU_PO2_Num\]](#)
- PaO2 (mmHg) [\[F07_LUNG_FUNCTION_ASS.LU_PaO2_Num\]](#)

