4.6 Secondary objective #2: Frequency of exacerbations during observation

Table 24. Exacerbations since IPF diagnosis

This table will describe the absolute and relative frequency distribution of patients with:

- at least one exacerbation during observation period since IPF diagnosis [\[F08_EXACERBATIONS.EX_Exacerbation_YN\]](#)
- at least one mild, moderate, severe exacerbation during observation period since IPF diagnosis [\[F08_EXACERBATIONS.Ex_exacer_1-10_Severity\]](#)

Percentages will be computed out of the total number of patients evaluable at enrollment.

The table will provide the descriptive statistics (mean, median, standard deviation, quartiles, min, max) of

- number of exacerbations per patient since IPF diagnosis during observation period (as defined in “Computed variables” chapter)
- number of exacerbations per patient since IPF diagnosis during observation period stratified by exacerbation severity [\[F08_EXACERBATIONS.Ex_exacer_1-10_Severity\]](#)

Descriptives will be calculated out of the number of patients evaluable at enrollment.

4.7 Secondary objective #3: Health related quality of life (HRQoL) variation during 12 months of observation

Table 26. EQ-5D-5L distribution of items of descriptive system and VAS during observation

The table will provide at enrollment, V3, V5:

- Frequency or the proportion of reported problems for each level for each dimension: mobility, self-care, usual activity, pain/discomfort, anxiety/depression [F11_EQ_5D_5L.EQ_5d_1-EQ_5D_5]
- main descriptive statistics (mean, median, standard deviation, quartiles, min, max) of EQ VAS [F11_EQ_5D_5L.EQ_5d_6_NUM]

Descriptives will be calculated over the number of patients who performed each visit with EQ-5D-5L filled in.

Higher index and VAS scores mean better QoL.

Table 27. St.Georges Respiratory Questionnaire (SGRQ)

The table will provide at enrollment, V3, V5 the descriptive statistics (mean, median, standard deviation, quartiles, min, max) of the:

- 3 components scores of SGRQ: symptoms, activities and impacts on daily life;
- total score (as defined in "Computed variables" chapter).
- change at each follow-up visit vs baseline of symptoms, activities and impacts on daily life scores;
- change at each follow-up visit vs baseline of total score.

Descriptives will be calculated over the number of patients who performed each visit with SGRQ filled in.

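### A follow-up visit counts as performed only if the symptom item is valid at baseline and at that visit, so tables that do not need that item can undercount visits, drop completed questionnaires and use the wrong treatment denominator

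*SAP*

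**What the plan says.** SAP section 3 (Computed variables) lists four criteria for having performed a follow-up visit, and all must be met:

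1. The patient is evaluable at enrolment.
2. The field recording that data were collected at that visit is Yes.
3. The visit date lies within 1.5 months of the nominal time.
4. "With available IPF symptoms evaluation at baseline and at" the visit. The answer must be No, or Yes with at least one symptom recorded.

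The set defined this way is then used as follows:

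- Table 1 counts patients who performed V2 to V5: "The percentages will be computed over the total number of enrolled patients".
- Table 4 gives visit timing: "Patients who performed each follow up visit will be considered".
- Table 13 gives symptom frequency: "Descriptives will be computed out of the total number of patients who performed the specific visit".
- Table 26: "Descriptives will be calculated over the number of patients who performed each visit with EQ-5D-5L filled in".
- Table 27: "Descriptives will be calculated over the number of patients who performed each visit with SGRQ filled in".
- Tables 35-37, 39-41 and 46-48 take percentages of ongoing treatments out of the patients who performed the 3-, 6- or 12-month visit.

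Two other SAP rules bear on this. Section 4 says: "Missing data will not be imputed and so patients with missing data will be excluded from the analyses of that variable(s". Section 2.1, criterion 10, accepts a patient at enrolment on any one of symptoms (an mMRC score suffices), lung function or 6-minute walk distance.

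**The concern.** Criteria 1 to 3 already establish that the visit took place, on time, with data. Criterion 4 concerns one eCRF item, yet it decides whether the patient exists at that visit for outcomes recorded elsewhere.

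- **Disposition.** Table 1 would omit from its performed-visit counts a visit that took place in window with data collected. Table 4 would leave out its timing.
- **Quality of life.** Tables 26 and 27 already require the questionnaire to be filled in. There, criterion 4 can only remove patients who completed it.
- **Treatments.** The denominator shrinks. What follows depends on a numerator rule that the SAP does not state.
- **Symptoms.** Frequency at a visit needs that visit's answer only. Table 13 nevertheless loses recorded symptoms when only the baseline answer is missing.

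A blank at one visit affects that visit. A blank at baseline affects all four follow-up visits for that patient.

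**Working it through.** **Step 1: enrolment rule against visit rule.** The baseline symptom item has four states: No; Yes with a symptom named; Yes with none named; blank. The first two satisfy criterion 4 at baseline and the last two do not. Combine each state with mMRC, lung function and walk test present or absent (2 × 2 × 2 = 8 patterns):

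- Valid item: 2 × 8 = 16 patterns, all evaluable at enrolment.
- Invalid item: 2 × (8 − 1) = 14 patterns evaluable at enrolment through another measure.

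So 14 of the 30 evaluable patterns can never count at V2-V5. These are data patterns, not proportions of patients. The rules also differ on mMRC: it counts as symptom evidence at enrolment but not in criterion 4.

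**Step 2: effect per patient with an invalid baseline item.** No missingness rate is needed. Up to 4 visit counts are lost in Table 1, each worth 1/200 = 0.5 percentage points at its visit if 200 are enrolled. Up to 2 follow-up records per questionnaire are lost (V3 and V5). Up to 3 treatment denominators are reduced (3, 6 and 12 months).

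**Step 3: the treatment tables.** The definition headed "IPF pharmacological treatments ongoing at 3, 6 and 12-month follow-up visit", and its non-pharmacological counterpart, select therapies by therapy, diagnosis and visit dates. Neither mentions performed-visit status. The tables apply that status only to the denominator. Two readings are open: an unrestricted numerator inflates the percentage; a restricted one drops valid treatment data.

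**Step 4: illustration of size.** Protocol 8.5 plans 200 patients with 20% to 40% drop-out: 200 × (1 − 0.40) = 120 and 200 × (1 − 0.20) = 160, which reproduces its stated range at 12 months. I take these as patients meeting criteria 1 to 3. Let b and v be the shares with an invalid item at baseline and at the visit, assumed independent:

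- counted = n × (1 − b) × (1 − v)
- lost = n − counted
- inflation of a treatment percentage, if the numerator covers all n = 1 / [(1 − b)(1 − v)]

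The documents give no rate, so b = v below is assumed.

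| b = v | Counted at V5 | Lost | Table 1, % of 200 | Inflation factor |
|---|---|---|---|---|
| 0% | 120 to 160 | 0 | 60.0 to 80.0 | 1.000 |
| 1% | 117.6 to 156.8 | 2.4 to 3.2 | 58.8 to 78.4 | 1.020 |
| 2% | 115.2 to 153.7 | 4.8 to 6.3 | 57.6 to 76.8 | 1.041 |
| 5% | 108.3 to 144.4 | 11.7 to 15.6 | 54.15 to 72.2 | 1.108 |
| 10% | 97.2 to 129.6 | 22.8 to 30.4 | 48.6 to 64.8 | 1.235 |

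With blanks at baseline only, 2% to 5% would lose 120 × 0.02 = 2.4 to 160 × 0.05 = 8.0 patients, or 1.2 to 4.0 percentage points in Table 1. Visit-level blanks add to that, so it is not an upper limit.

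**The case against.** The best defence is that symptoms are part of the primary objective, and that a set with both baseline and visit answers lets each visit be compared with baseline. A single visit denominator shared by tables is also a legitimate choice. This stands for incident and remitted symptoms, which the SAP defines directly afterwards. It does not carry over to questionnaires, treatments or disposition, and nothing in the available SAP text confines the set to symptom tables.

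Second, blanks may be rare. The item is scheduled at every visit, a plain No satisfies it, and Protocol 8.6 provides edit checks and queries. This stands: the effect may be nil.

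Third, without criterion 4 a visit with no outcome data might count as performed. Criterion 2 already requires the data-collected flag, and each outcome table can require its own variable, so this does not defeat the change.

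Some stronger readings are tempting but unsupported:

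- A reader might infer that treatment records are certainly lost. The SAP restricts only the denominator in words, and Tables 42, 49 and 50 still report treatment in patients evaluable at enrolment.
- A reader might infer a breach of Protocol 8.7, which keeps patients with missing values. That section analyses evaluable patients without defining the term for follow-up visits, so there is tension rather than clear contradiction.
- A reader might extend the point to lung function and walk distance. Tables 20-22 use a different term, evaluable patients at the specific visit, whose definition is not in the available text. No claim is made about them.

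**Conclusion.** The point holds on the wording. Criterion 4 is a joint condition, and the set it defines is reused where the symptom form is irrelevant, contrary to the SAP's rule limiting exclusion to the variable that is missing. The loss of completed questionnaires and the undercount of visits follow directly whenever the item is invalid. For treatments, the result is either inflated percentages or dropped data, depending on how the numerator is programmed.

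The size cannot be established from the documents. The illustrative figures rest on assumed rates and independence, and none is a maximum. It would be wrong to read them as an expected loss or to infer an overall direction of bias. Enrolment values are unaffected, as are tables based on patients evaluable at enrolment (24, 28-33, 42, 49, 50, 52) and withdrawals in Table 3. The change should be made because the condition is unnecessary in the affected tables and cheap to remove, not because a large distortion has been shown.

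**What to change.** - Define performed visit x by criteria 1 to 3 only.
- For Table 13, require a valid symptom answer at the visit. Require the baseline answer in addition only for incident and remitted symptoms.
- In Tables 26 and 27, require only the questionnaire at the visit, and its baseline value for change scores. Apply the same principle to the other affected tables.
- In Tables 35-37, 39-41 and 46-48, state that numerator and denominator are drawn from the same patients.
- State what evaluable at the specific visit means in Tables 20-22. If it relies on the present definition, make the same change there.

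The cost is SAP wording and a small change to the analysis-set code, with no new data. Denominators will differ slightly between tables. The missing-data frequencies planned in Protocol 8.7 already provide the means to report this.

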An exacerbation will be considered occurred during observation period if onset date **[F08_EXACERBATIONS.Ex_Exacer_1_Ons_date-Ex_Exacer_10_Ons_date]** >=date of first IPF diagnosis (mm/yyyy) **[F05_DIAGNOSIS_IPF.DIA_Date_IPF_diagnosis]** and onset date **[F08_EXACERBATIONS.Ex_Exacer_1_Ons_date-Ex_Exacer_10_Ons_date]** <= last available visit date **[P16_PATIENT_DISPOSITION.PD_2]** (for patients who completed the study **[F19_STUDY_COMPLETION.SC_1]** = Yes) OR date of Date of drop out or death **[F19_STUDY_COMPLETION.SC_4, SC_5]** (for patients who did not complete the study **[F19_STUDY_COMPLETION.SC_1]** = No).

Health Related Quality of Life (HRQoL) EQ-5D-5L (see Appendix 8.3)

The EQ-5D-5L is a standardized measure of health status, it is filled in by patients. It consists of 2 sections: "EQ-5D descriptive system" and EQ visual analogue scale (EQ VAS).

²Perez T. et al. Modified Medical Research Council scale vs Baseline Dyspnea Index to evaluate dyspnea in chronic obstructive pulmonary disease *Int J Chron Obstruct Pulmon Dis.* 2015; 10: 1663-1672.

The EQ-5D-5L descriptive system comprises the following 5 dimensions: mobility, self-care, usual activities, pain/discomfort and anxiety/depression.

The EQ VAS indicate the health status self-assessed by the patient on a visual analogue scale from 0 to 100, where 100 is the "best imaginable health state" and 0 the "worst imaginable health state". It can be used as a quantitative measure of health as judged by respondents.

St. George's Respiratory Questionnaire (SGRQ) (see Appendix 8.5)

The SGRQ is designed to measure health impairment in patients with asthma and COPD.

There is a report of its validation in a small study of adults with cystic fibrosis (Archivos de Bronconeumologia Volume 43, Issue 4, April 2007, pages 205-211). It is in two parts. Part 1 produces the Symptoms score, and Part 2 the Activity and Impacts scores. A Total score is also produced.

Part 1 (Questions 1-8) addresses the frequency of respiratory symptoms. It is not designed to be a precise epidemiological tool, but to assess the patient's perception of their recent respiratory problems.

Part 2 (Sections 9-17) addresses the patient's current state (i.e. how they are these days).

The Activity score measures disturbances to daily physical activity. The Impacts score covers a range of disturbances of psycho-social function. Validation studies for the original SGRQ showed that this component relates in part to respiratory symptoms, but it also correlates quite strongly with exercise performance (6-minute walking test), breathlessness in daily life (MRC breathlessness score) and disturbances of mood (anxiety and depression). The Impacts score is, therefore, the broadest component of the questionnaires, covering the whole range of disturbances that respiratory patients experience in their lives.

Three component scores are calculated: Symptoms; Activity; Impacts

One Total score is also calculated.

PRINCIPLE OF CALCULATION

Each questionnaire response has a unique empirically derived 'weight'. The lowest possible weight is zero and the highest is 100.

Each component of the questionnaire is scored separately in three steps:

i. The weights for all items with a positive responses are summed.

ii The weights for missed items are deducted from the maximum possible weight for each component. The weights for all missed items are deducted from the maximum possible weight for the Total score.

iii. The score is calculated by dividing the summed weights by the adjusted maximum possible weight for that component and expressing the result as a percentage:

Score = 100 x Summed weights from positive items in that component /Sum of weights for all items in that component

The Total score is calculated in similar way:

Score = 100 x Summed weights from positive items in the questionnaire/Sum of weights for all items in the questionnaire

Sum of maximum possible weights for each component and Total:

Symptoms	662.5
Activity	1209.1
Impacts	2117.8
Total	3989.4

(Note: these are the maximum possible weights that could be obtained for the worst possible state of the patient). For more details see: http://www.healthstatus.sgul.ac.uk/SGRQ_download/SGRQ%20Manual%20June%202009.pdf

IPF pharmacological treatments ongoing at enrollment

IPF pharmacological treatments from diagnosis and ongoing at enrollment will be defined as follows.

All IPF pharmacological treatments having (Start date of therapy (dd/mmm/yyyy) **[F23_IPF_PHARMACOLOGICAL_THERAPY.START_DATE_THER]** >= date of first IPF diagnosis (mm/yyyy) **[F05_DIAGNOSIS_IPF.DIA.Date_IPF_diagnosis]** AND Start date of therapy (dd/mmm/yyyy) < Date of enrollment visit) AND (end date (dd/mmm/yyyy) **[F23_IPF_PHARMACOLOGICAL_THERAPY.END_DATE_THER]** > Date of enrollment visit (dd/mmm/yyyy) **[PatientInfo.Date_enrollment]** OR (end date missing AND "Ongoing at the end of observation?" = "Yes")) will be considered.

Drug names will be coded by CDM in actives.

IPF pharmacological treatments ongoing at 3, 6 and 12-month follow-up visit

IPF pharmacological treatments from diagnosis and ongoing at 3-, 6- or 12-month follow up will be defined as follows.

At each follow-up visit all treatments having (start date **[F23_IPF_PHARMACOLOGICAL_THERAPY.START_DATE_THER]** >= date of first IPF diagnosis (mm/yyyy) **[F05_DIAGNOSIS_IPF.DIA.Date_IPF_diagnosis]** AND < date of follow-up visit) AND ((end date **[F23_IPF_PHARMACOLOGICAL_THERAPY.END_DATE_THER]** >= date of first IPF diagnosis (mm/yyyy) **[F05_DIAGNOSIS_IPF.DIA.Date_IPF_diagnosis]** AND end date > date of follow-up visit **[F16_PATIENT_DISPPOSITION.PD_2]**) OR (end date = missing and "Ongoing at the end of observation?" = "Yes" **[F23_IPF_PHARMACOLOGICAL_THERAPY.ONGOING_THER]**) will be selected.

IPF non-pharmacological therapy ongoing at enrollment

IPF non pharmacological treatments from diagnosis and ongoing at enrollment will be defined as follows.

All IPF non-pharmacological therapy having (Start date of therapy (dd/MMM/yyyy) **[F24_NON_PHARMACOLOGICAL_THERAPY.START_DATE_NF]** >= date of first IPF diagnosis (mm/yyyy) **[F05_DIAGNOSIS_IPF.DIA_Date_IPF_diagnosis]** AND Start date of therapy (dd/MMM/yyyy) < Date of enrollment visit) AND (end date (dd/MMM/yyyy) **[F24_NON_PHARMACOLOGICAL_THERAPY.END_DATE_NF]** > Date of enrollment visit (dd/MMM/yyyy) **[PatientInfo.Date_enrollment]**) OR (missing and "Ongoing at the end of observation?" **[F24_NON_PHARMACOLOGICAL_THERAPY.ONGOING_NF_THER]** = "Yes")) will be considered.

For patients receiving more than one therapy, combination of therapies will be reported (e.g. Long-term oxygen therapy + Cardiopulmonary exercise training).

IPF non pharmacological treatments ongoing at 3-, 6- and 12-month follow-up visit

IPF non pharmacological treatments from diagnosis and ongoing at 3-, 6- or 12-month follow up will be defined as follows.

At each follow-up visit all treatments having (start date **[F24_NON_PHARMACOLOGICAL_THERAPY.START_DATE_NF]** >= date of first IPF diagnosis (mm/yyyy) **[F05_DIAGNOSIS_IPF.DIA_Date_IPF_diagnosis]** AND < date of follow-up visit) AND ((end date **[F24_NON_PHARMACOLOGICAL_THERAPY.END_DATE_NF]** >= date of first IPF diagnosis (mm/yyyy) **[F05_DIAGNOSIS_IPF.DIA_Date_IPF_diagnosis]** AND end date > date of follow-up visit **[F16_PATIENT_DISPOSITION.PD_2]**) OR (end date = missing and "Ongoing at the end of observation?" = "Yes") **[F24_NON_PHARMACOLOGICAL_THERAPY.ONGOING_NF_THER]**) will be selected.

Patients with AEs or ADRs during observation period

Are defined as patients with at least one AEs or ADRs between diagnosis and end of observation defined as events with date of diagnosis <= start date AE <= date of last available follow up.

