8.5 STUDY SIZE

The sample size was determined on the basis of feasibility criteria. In fact, according to the volume of patients managed by the centers involved in this study, inclusion of 200 subjects (10 patients/center) with the characteristics defined at Inclusion/Exclusion criteria paragraphs is deemed reasonable for enrolment period (18 months).

An evaluation of the possible achievable precision of the estimates was performed considering the primary objective of the study and literature data, when available.

The primary objective of the study is to describe the clinical course during 12 months of observation, in terms of symptoms, lung function and exercise tolerance. Assuming a drop-out rate ranging from 20% to 40%, the total number of evaluable patients at 12-month follow-up visit is expected to range between 120 and 160 subjects. Drop-out rate was hypothesized by considering mortality rate in IPF patients and natural drop-out from studies. Literature data about the clinical course of outcomes of interest in IPF patients in a real-life context are scanty. Nishiyama et al. [35] conducted a study on 93 IPF patients and assessed the pulmonary function. The mean (\pm SD) of FVC, FEV1, DLCO were 2.37 (\pm 0.73) L, 1.93 (\pm 0.57) L and 9.19 (\pm 3.92) mL*min⁻¹*mmHg⁻¹ respectively. According to the data of a recently completed trial on patients with IPF by Swigris et al [37], the mean (\pm SD) baseline

6-min walked distance was 372.9 (± 82.63) meters. Regarding the most common IPF symptoms, clubbing, dyspnea (evaluated by means of a mMRC score ≥ 2), crackles and cough frequencies are 43%, 44%, 67% and 73% respectively [34, 35].

Table 1 shows the two-sided 95% confidence interval (CI) for expected frequency of IPF symptoms for a sample size n=120 and 160, using the large sample normal approximation [36].

| | Expected frequency | 95% CI | | | |
|--------------------------------|--------------------|--------|-------|--|--|
| IPF symptoms | | | | | |
| n=120 | | | | | |
| Clubbing | 43% | 34.1% | 51.9% | | |
| Dyspnea (mMRC score ≥ 2) | 44% | 35.1% | 52.9% | | |
| Crackles | 67% | 58.6% | 75.4% | | |
| Cough | 73% | 65.1% | 80.9% | | |
| n=160 | | | | | |
| Clubbing | 43% | 35.3% | 50.7% | | |
| Dyspnea (mMRC score ≥ 2) | 44% | 36.3% | 51.7% | | |
| Crackles | 67% | 59.7% | 74.3% | | |
| Cough | 73% | 66.1% | 79.9% | | |

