4.14 AEs and ADRs between diagnosis and end of observation**Table 52. Patients with AEs and ADRs between diagnosis and end of observation**

The table will provide the absolute and relative frequency of the patients with at least one adverse events between diagnosis and end of observation.

The total number of evaluable patients at enrollment will be considered.

Listing 53. AEs and ADRs between diagnosis and end of observation

The table will provide the distribution of every AE or ADR, occurred between diagnosis and end of observation by serious AE, seriousness category and causal relationship with Nintedanib.

The total number of evaluable patients at enrollment will be considered.

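### SAP section 3 gives the adverse-event window no end-point for non-completers, so Table 52 probably omits recorded events that start between the last visit and drop-out or death

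*SAP*

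**What the plan says.** SAP section 3 (Computed variables) defines patients with AEs or ADRs during the observation period through "events with date of diagnosis <= start date AE <= date of last available follow up". It attaches no eCRF variable to the upper limit and has one rule for all patients.

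The exacerbation definition in the same section splits the upper limit in two. For patients who completed the study it is the "last available visit date", tied to field PD_2. For those who did not, the text continues "OR date of Date of drop out or death", tied to fields SC_4 and SC_5 of the study-completion form.

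Two outputs in SAP 4.14 depend on the AE window:

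- Table 52 reports "patients with at least one adverse events between diagnosis and end of observation".
- Listing 53 gives the "distribution of every AE or ADR, occurred between diagnosis and end of observation". It does not cite the section 3 definition, so only the shared wording links the two.

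The base for Table 52 is set by "The total number of evaluable patients at enrollment will be considered", so non-completers stay in it.

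Protocol 8.5 plans for 200 patients, "Assuming a drop-out rate ranging from 20% to 40"%. It explains that "Drop-out rate was hypothesized by considering mortality rate in IPF patients and natural drop-out from studies".

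**The concern.** Two event types in the same patient appear to be followed for different lengths of time. For a patient who dies or leaves between visits, an exacerbation is counted up to the exit date. An AE seems to be counted only up to the last visit. The time left out is the time just before exit, in a cohort where deaths are an expected part of drop-out.

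At stake is the percentage in Table 52 and, probably, the completeness of Listing 53, which classifies events by seriousness and by causal relationship with nintedanib. Because the SAP fragment names no date field, two programmers could also produce different tables from the same database.

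**Working it through.** **1. The two rules side by side (SAP section 3)**

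| | Exacerbations | AEs / ADRs |
|---|---|---|
| Lower limit | IPF diagnosis | IPF diagnosis |
| Upper limit, completers | last visit date [PD_2] | last follow-up, no field named |
| Upper limit, non-completers | drop-out or death [SC_4, SC_5] | no separate rule |

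**2. What the difference does, reading the AE limit as the last attended follow-up.** These are invented patients.

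- Patient A attends at months 3 and 6 and exits at month 8. An event starts at month 7. As an exacerbation: 7 ≤ 8, counted. As an AE: 7 ≤ 6 is false, not counted.
- Patient B exits at month 2, before Visit 2. There is no follow-up date, so no AE can meet the condition, yet the patient is in the Table 52 denominator.
- Patient C completes. Both rules end at the last visit, so nothing changes.

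Extending the window to exit can only add events, while the denominator is fixed. Any error in Table 52 is therefore downward.

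**3. How many patients are in the position of A or B.** Inputs: 200 patients and 20–40% drop-out (Protocol 8.5). The protocol's evaluable numbers reproduce: 200 × (1 − 0.20) = 160 and 200 × (1 − 0.40) = 120. Non-completers are therefore 200 − 160 = 40 to 200 − 120 = 80.

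**4. Time outside the window (illustration).** Visit spacing comes from Protocol 8.1. Assumptions not in the documents: exits are uniform over 12 months, and visits fall exactly at 3, 6 and 9 months and are all attended until exit.

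- Mean gap from last visit (or enrollment) to exit: 3 / 2 = 1.5 months.
- Time outside: 40 × 1.5 = 60 to 80 × 1.5 = 120 patient-months.
- Post-enrollment follow-up: 160 × 12 + 40 × 6 = 2160, and 120 × 12 + 80 × 6 = 1920 patient-months.
- Share outside: 60 / 2160 = 2.8% to 120 / 1920 = 6.3%.
- If half of the non-completers leave at a visit (gap zero): 30 / 2160 = 1.4% to 60 / 1920 = 3.1%.
- Missed visits, or exits concentrated late in an interval, would raise these figures, so they are not upper bounds.

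**5. Patients with no follow-up visit.** Exit before month 3 has probability 3 / 12 = 25%, giving 10 to 20 patients. If Visit 2 falls anywhere in its 2–4 month window, the range is 40 × 2/12 ≈ 7 to 80 × 4/12 ≈ 27.

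**6. Effect on Table 52.** Taking all 200 as evaluable, each patient whose only recorded AE falls in the gap lowers the percentage by 1 / 200 = 0.5 points. For the group exiting before Visit 2, if a share q had a recorded AE, the shortfall is (10 to 20) × q / 200, or 5q to 10q points. That is 0.5–1.0 points at q = 10% and 2.5–5.0 points at q = 50%. Both values of q are assumed. The documents give no AE rate from which to derive q or the number of AEs lost.

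**The case against.** The strongest reply is that nothing has been shown to be omitted. The upper limit is worded differently from the visit date in the exacerbation rule, and the definition concerns the observation period, which that rule already carries to drop-out or death. A programmer could fairly include an exit date. The public SAP is also incomplete (its section numbers jump), so a definition may stand in text that was removed. Both points stand: the omission depends on a reading. That reading remains the likelier one, because the SAP regularly uses follow-up to mean a scheduled visit and spells out the exit-date branch when it wants one.

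A second reply is that a visit-based cut-off is defensible, since the schedule in Protocol 8.3 collects AEs at Visits 2–5 and later recording will be patchy. This limits the likely size. It does not explain the difference, because exacerbations are scheduled at those same visits and are still counted to exit. Protocol 10.2 also has ADRs and fatal AEs under the sponsor's product collected until the end of the study, so later entries can be in the database.

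A reader might infer that deaths disappear from the results. The documents do not support that. Study exits and their causes are tabulated in SAP Table 3, death dates are held on the study-completion form, and fatal AEs under the sponsor's product go through expedited reporting (Protocol 10.2). An AE that starts before the last visit and later proves fatal is still counted.

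Nor do the figures mean that 40–80 patients lose an AE. That is the number of expected non-completers. Table 52 changes only for those whose sole recorded AE starts in the gap.

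**Conclusion.** The point holds as a minor one. The AE/ADR definition lacks the non-completer branch that the exacerbation definition has. On the likely reading, Table 52 is too low by an amount that cannot be computed from the documents, and Listing 53 is probably cut at the same date. The scale is 40–80 expected non-completers and, under even exits and exact 3-monthly visits, 60–120 patient-months and 10–20 patients with no follow-up visit. Those figures describe time and patients at risk of omission, not lost events.

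The effect is confined to one frequency table and probably one listing. AEs are not among the primary or secondary objectives.

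**What to change.** In SAP section 3, set the upper limit for AEs and ADRs to the last visit date [PD_2] for completers and to the date of drop-out or death [SC_4, SC_5] for non-completers, as for exacerbations. Add that this definition governs both Table 52 and Listing 53. If a visit-based cut-off was intended, say so and explain why it differs from the exacerbation rule.

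The cost is a sentence or two of SAP text. The date fields are already used in the same section, and no new data are needed.
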